#### Specific Aim 1b:

This aim will use clinical outcomes data from a previously recruited CITA cohort of 445 acamprosate-treated alcoholic patients and metabolomics data obtained with two metabolomics analytical platforms to identify metabolomic markers associated with length of sobriety as well as additional secondary phenotypes identified in Aim 1a. We will then apply a “pharmacometabolomics-informed pharmacogenomics” research strategy in which we will perform genome-wide association studies in search for genetic variants associated with metabolites associated with acamprosate clinical outcomes. We will pursue all signals, genes and pathways functionally and mechanistically in order to investigate the biological mechanisms underlying sobriety length and other phenotypes associated with acamprosate treatment response. This is the same approach that we used previously with success to study biological mechanisms contributing to effects of selective serotonin reuptake inhibitors in patients with major depressive disorder (MDD).

Specific Aim 2: To identify genetic and metabolomic biomarkers associated with acamprosate response in the new cohort of 800 alcoholic patients randomized to acamprosate or placebo treatment.

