### Study flow and Schedule of Events

Study personnel will explain the research risks and benefits. Written informed consent will be obtained for each study subject. The baseline diagnostic assessment, triage, treatment group assignment and follow up assessments are summarized in Fig. 1 and described in more detail in Specific Aim 2. Information regarding severity of alcohol withdrawal symptoms (measured by CIWA scale or site specific equivalent method) and medications used during withdrawal treatment preceding enrollment in the study will be collected or abstracted from the medical record and included in the data analyses.

\*Notation dated 5-12-2023: Upon IRB approval, subjects will no longer be randomized to the placebo arm. Instead, for the remainder of the study, all patients will be provided acamprosate to achieve the active drug and placebo ratio of 2:1.

Figure 1: Study Flow Chart

The presence of AUD and other psychiatric disorders will be confirmed by a computer version of the Psychiatric Research Interview for Substance and Mental Disorders (PRISM) [24]. The presence of comorbid depressive disorders requiring treatment will be determined by the combination of 2 characteristics: (1) the presence of any

diagnosis of depression during the previous year as confirmed by PRISM and verified by the study psychiatrist; and (2) a PHQ-9 score of 10 or above and/or a GAD-7 score of 10 or above. The interview will be conducted by interviewers trained and certified on the use of the PRISM. Interviewers, who have submitted required recordings and documents for certification and an unexpected delay in the certification process occurs, will be allowed to conduct prism assessment, if no other certified staff are available, with certification pending. The research pharmacy contracted for this study will randomize the study participants for all sites with placebo or acamprosate.

The schedule of study procedures and assessments is tabulated by visit in the Study Assessments in Table 1 (below). A visit window of +/- 10 days is allowed when scheduling. Questionnaires may be distributed in multiple formats (paper, electronic/mailed link, or asked/read to patient).

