#### Inclusion Criteria:

1. Age 18 to 85; DSM-5 (14) diagnosis of AUD determined by PRISM;
2. Completion of alcohol detoxification (CIWA score < 5) and no alcohol for at least 7 days (but no more than 35 days);
3. Ability to provide informed consent
4. Ability to speak English
5. Willingness to use the study medications for 3 months and attend follow-up visits.
6. No chronic/daily use of benzodiazepines, opioids, or stimulants for a period of time which is determined by 3 x the medication half-life value (see addendum A) to be completed before the initiation of study medication (acamprosate or placebo).
7. Willingness to discontinue previously prescribed acamprosate for a period of at least 3 days before randomization to study medication (acamprosate or placebo\*) which allows for metabolomic signature without medication.

\*Notation dated 5-12-2023: Upon IRB approval, subjects will no longer be randomized to the placebo arm. Instead, for the remainder of the study, all patients will be provided acamprosate to achieve the active drug and placebo ratio of 2:1.

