#### Analysis for Specific Aim 1b

Metabolite concentrations will be log-2 transformed, and associations between baseline metabolite concentrations and the time of abstinence since baseline will be evaluated by linear regression with age and gender as covariates. If Timeline Follow Back (TLFB) data at 3-months is absent, the date of last contact will serve as the day of first lapse unless the subject has reported a lapse at an earlier time point. To study the possible effect of depression severity and liver function, regression models including baseline PHQ-9 scores and LFTs (AST, ALT, and GGT) will be compared with those without to determine whether the metabolites remain significantly correlated with treatment outcome. Participants who provided paired blood samples will be classified as responders (maintenance of complete abstinence) or non-responders (any consumption of alcoholic beverages during the trial period), and their metabolite concentrations at baseline and at 3 months will be compared by two-way ANOVA to detect any significant changes between the two time points and whether these changes differ significantly between groups.

After metabolomic markers associated with length of sobriety (or additional secondary phenotypes) are identified, we will apply a “pharmacometabolomics-informed pharmacogenomics” research strategy. Specifically, we will perform genome-wide association analyses to search for genetic variants associated with metabolites that are associated with acamprosate clinical outcomes. We will then evaluate the association of the identified genetic variants ( $p < 5 \times 10^{-8}$ ) with clinical treatment outcomes in all available datasets (including the COMBINE and PREDICT datasets used in Aim 1a). We will also pursue all signals, genes and pathways functionally and mechanistically in order to investigate the biological mechanisms underlying sobriety length and other phenotypes associated with acamprosate treatment response. This is the same approach that we used previously with success to study biological mechanisms contributing to effects of selective serotonin reuptake inhibitors in patients with major depressive disorder (MDD).

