Table 2 Subject Characteristics	COMBINE	PREDICT	CITA
N	1393	426	443
Age, mean(SD)	44.4 (10.2)	45.3 (8.7)	42.1 (11.8)
Sex, N(%) male	955 (69%)	328 (77%)	286 (65%)
Race, N(%) white non-Hispanic	1062 (77%)	426 (100%)	412 (93%)
Baseline Consumption Measures (last 30 days)			
Average drinks per drinking day	13.0 (8.1)	19.4 (11.3)	11.8 (7.7)
% drinking days	72.8 (23.5)	82.1 (1.3)	50.7 (29.7)
% heavy drinking days	65.2 (24.9)	79.0 (1.3)	45.8 (29.7)
Number of days since last drink	7.7 (5.3)	22.1 (4.4)	24.8 (16.1)
Medications			
Acamprosate, N	608	172	443
Naltrexone, N	614	169	0
No active drug (placebo or no medication), N	466	85	0
Treatment outcomes			
3 month abstinence from any drinking, N(%)	293 (21.2)	194 (45.5)	132 (29.7)
3 month abstinence from heavy drinking, N(%)	432 (31.2)	210 (49.3)	168 (37.9)

For COMBINE and CITA, baseline consumption is based on 30 days prior to the start of medication, while for PREDICT it is based on 30 days prior to the onset of inpatient treatment, as proposed by Mann and colleagues (84).

For the COMBINE study, the number of participants for each medication may include participants on more than one medication (i.e. groups are not mutually exclusive since the study included acamprosate/naltrexone co-treatment).

Numbers for treatment outcomes are based on the ITT sample (i.e. complete sample) assuming those who dropped out prior to 3 months had returned to heavy drinking.

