#### Analysis for Specific Aim 2b:

Analysis for Aim 2b will use a similar strategy the analysis described above in aim 1b. However, in Aim 2b analyses will be performed on the much larger new sample and will also include assessment of drug interactions to evaluate whether metabolomics predictors of treatment outcome differ between acamprosate-treated and placebo-

treated patients. After identifying metabolites that predict treatment outcomes, we will again apply a pharmacometabolomics-informed pharmacogenomics analysis strategy, but genetic associations will be evaluated in the full sample of patients with genetic and treatment outcomes data, including the existing samples used in Aim 1 and the new samples collected in Aim 2.

Analysis for Specific Aim 3 will be completed in the future utilizing the latest methodology and analyses.

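### The metabolite–sobriety regressions in Aims 1b and 2b do not name days since last drink as a covariate, so recency of drinking can confound the baseline metabolite associations

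*Combined protocol and SAP*

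**What the plan says.** Data Analysis, Analysis for Specific Aim 1b, studies "associations between baseline metabolite concentrations and the time of abstinence since baseline" in the "previously recruited CITA cohort of 445 acamprosate-treated alcoholic patients" (Table 2 gives 443). In the main model these associations "will be evaluated by linear regression with age and gender as covariates". As a check on depression severity and liver function, "regression models including baseline PHQ-9 scores and LFTs (AST, ALT, and GGT) will be compared with those without". The responder versus non-responder ANOVA in the same section names no covariates.

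For the new trial, "Analysis for Aim 2b will use a similar strategy the analysis described above in aim 1b", with drug interactions added.

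The missing variable appears elsewhere:
- Table 2 has a row headed "Number of days since last drink": 24.8 (SD 16.1) in CITA.
- Inclusion criterion 2 of the new trial requires "no alcohol for at least 7 days (but no more than 35 days", so the date of last drink must be established for every entrant.
- Table 1 schedules the TLFB at baseline.

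Study flow and Schedule of Events says that withdrawal severity and withdrawal medications will be collected or "abstracted from the medical record and included in the data analyses". It names no model for them and does not mention time since last drink.

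**The concern.** In an alcohol trial, how recently a person drank can plausibly shift the baseline metabolite profile and also the chance of staying sober. The outcome clock starts at baseline, so abstinence before baseline is not part of the outcome and is not otherwise accounted for. A metabolite that merely tracks recency could then be selected as a marker of sobriety length and passed on to the GWAS and functional work. If the two correlations had opposite signs to a true effect, a real marker could be masked instead.

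The plan already takes care over other influences on the metabolome. It asks for previously prescribed acamprosate to be stopped before randomization, and it excludes advanced liver disease partly because of its effect on metabolomic findings. Recency of drinking deserves the same treatment.

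**Working it through.** The plan states no power, alpha or sample-size figure for these regressions, so there is nothing of its own to reproduce.

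**Inputs from the documents.** CITA N = 443 (Table 2) or 445 (Specific Aim 1b). Days since last drink in CITA: mean 24.8, SD 16.1. New-trial entry range: 7 to 35 days.

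**Assumed inputs.** Two-sided alpha of 0.05. Correlation of recency with the metabolite (a) and with sobriety length (b), each from 0.1 to 0.3.

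**Step 1, spread.** The coefficient of variation in CITA is 16.1/24.8 = 65%. In the new trial the allowed range is 35/7 = 5-fold. If uniform over 7 to 35 days (assumption), the SD is 28/√12 = 8.1 days.

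**Step 2, rejection rate without the covariate.** If the metabolite has no association with sobriety beyond recency, the induced correlation is r = a × b. With two covariates the Fisher z shift is δ = atanh(r) × √(N − 5). At N = 443, √438 = 20.93. The rejection rate is Φ(δ − 1.96) + Φ(−δ − 1.96).

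| a, b | r | δ | Rejection rate |
|---|---|---|---|
| 0.1, 0.1 | 0.01 | 0.21 | 5.5% |
| 0.2, 0.2 | 0.04 | 0.84 | 13% |
| 0.3, 0.2 | 0.06 | 1.26 | 24% |
| 0.3, 0.3 | 0.09 | 1.89 | 47% |

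N = 445 agrees to within 0.2 percentage points.

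**Step 3, with the covariate.** In a simulation (4,000 runs per scenario, N = 445), the model with age and gender alone rejected 24% of the time at 0.3 and 0.2, and 48% at 0.3 and 0.3. With days since last drink added, the rates were 5.2% and 5.5%.

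**Step 4, new trial.** Entry limits shrink the spread: u = 8.1/16.1 = 0.50. Under the usual range-restriction formula, r′ = ru/√(1 − r² + r²u²), a CITA correlation of 0.3 becomes about 0.16 and 0.2 becomes about 0.10. Squaring these and multiplying by √800 gives shifts of about 0.69 and 0.29, so the rejection rates at N = 800 are about 11% and 6%. These rest on the uniform assumption as well as on the correlations.

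**Step 5, cost if recency is unrelated to outcome.** If recency correlates 0.3 with the metabolite but not with sobriety, the standard error rises by a factor of 1/√(1 − 0.09) = 1.048, about 5%.

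**Step 6, is the variable well defined?** Footnote 1 of Table 2 bases CITA consumption on the 30 days before medication. If days since last drink (D) ran to the same date, drinking days in that window could not exceed max(0, 30 − D). For any distribution with mean 24.8 and SD 16.1, the mean of that quantity is at most ½[√(16.1² + 5.2²) + 5.2] = ½[16.9 + 5.2] = 11.1 days, or 37% of 30. Table 2 reports 50.7% drinking days, so the two rows appear to use different reference dates.

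**The case against.** The strongest reply has four parts.

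**The list is not closed.** A reader might infer that only age and gender can ever enter. The text does not say so: it names PHQ-9 and liver function comparison models (GGT may partly reflect drinking), Aim 2b is similar rather than identical, and withdrawal data are to be analysed. This stands. Still, none of these names time since last drink.

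**Later steps filter false leads.** Variants must reach p < 5 × 10⁻⁸ for the metabolite and are then tested against clinical outcomes in all datasets. Aim 2b seeks replication and tests drug interaction. These steps limit the harm, but they do not remove a recency-driven association at the selection step, and a confounded association can replicate when the same covariate is left out again.

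**A proxy still predicts.** Under the assumed correlations the marginal association is real, so for pure prediction it is not a false positive. That is fair, but the plan also wants biological mechanism, and a stand-in for a calendar question does not supply it.

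**Adjustment may remove signal.** Days since last drink precede the baseline draw, so they are not on a path from that measured level to later sobriety. A stable metabolic trait that had already helped the person abstain could be partly adjusted away, which is a reason to report both models.

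Three wider inferences are tempting but unsupported:
- The differing cohort means in Table 2 (7.7, 22.1, 24.8 days) cannot confound regressions run within CITA or within the new trial.
- Adjustment does not always gain precision (step 5).
- The point does not extend to Aim 2a or the meta-analysis. Recent drinking cannot alter germline genotype, and the Aim 2a text already allows adjustment for relevant covariates.

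**Conclusion.** The gap is real but modest. No metabolite model in Aims 1b or 2b names days since last drink, although it is available and varies widely in CITA. It can confound; the documents do not show that it does, because they give no correlation with any metabolite or with sobriety.

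The size depends wholly on the assumed correlations and alpha. In CITA, rejection of a non-predictive metabolite runs from a negligible 5.5% (0.1 and 0.1), through 13% (0.2 and 0.2), to 47% (0.3 and 0.3), against about 5% with the covariate. A reader might carry the CITA correlations unchanged to 800 patients and infer a larger problem there. The 7 to 35 day entry limit argues against that, and the effect in Aim 2b is probably smaller.

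**What to change.** In the Aim 1b and 2b metabolite models, prespecify days since last drink, counted to the baseline blood draw, as a covariate. Baseline drinking (for example percent heavy drinking days) may be added. Report each metabolite association with and without the adjustment, and say which result decides whether a metabolite goes forward to the GWAS.

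Before that, reconcile the reference dates in Table 2, where 24.8 days since last drink sits beside 50.7% drinking days in the last 30.

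The cost is analysis-plan wording and that data check. No new data collection is needed. The statistical downside is a small loss of precision (standard error up about 5% at a correlation of 0.3) if recency relates to the metabolite but not to the outcome.

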#### Specific Aim 3:

To apply a **systematic multiple-omics research strategy** to identify molecular and genomic signatures for all AUD samples mentioned in aims 1 & 2, as well as mechanisms underlying individual variation in response to acamprosate. To achieve this goal, we will obtain transcriptomic profiling and proteomic profiling for AUD subjects before and after 3 months of acamprosate therapy. We will then integrate the multiple omics datasets—

i.e., genomics, metabolomics, transcriptomics and proteomics—using machine learning approaches to develop a predictive algorithm for acamprosate response in patients with AUD.

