Other location's (Mayo Clinic Rochester & Hazelden Betty Ford, Center City, MN) patients' blood volume per blood draw: 50ml at Baseline (preferred but can be done at any visit) and 35 ml at Months 1 & 3

Hazelden Center City will offer participants to provide the additional ~15ml of blood as optional (preferred at baseline visit but can be done at any visit) for generation of the induced pluripotent stem cells (iPSCs) from peripheral blood mononuclear cells (PBMC) as described below.

Frequency of blood draw: three time points, Baseline, 1 and 3 month visits.

Blood samples for 35ml collection are for GGT levels: Serum Separator Tube (SST); DNA extraction, Acamprosate blood levels, Metabolomic, Proteomic biomarkers (EDTA tubes), and mRNA (PAXGene tube). The process of spinning and aliquoting the samples will be completed at each site. EDTA tubes that would need to be kept on ice, centrifuged in the cold (NOT frozen) with the plasma aliquoted into 200 ul aliquots which would need to be immediately placed and stored at minus 80 degrees. The current metabolomic platform would include both the amines and neuromodulators. Acamprosate blood drug levels will be plasma aliquoted into 300 ul aliquots and also assayed with these samples. PAXGene tube is placed directly into the minus 80 degree freezer.

An additional 15 ml of blood collected in EDTA tubes for peripheral blood mononuclear cells (PBMC) isolation. The separation and banking of PBMCs will be performed in the laboratory, frozen and stored in liquid nitrogen. PBMC are used to generate induced pluripotent stem cells (iPSCs), a cell type that can self-renew and which can be differentiated into many cell types from many human tissues.

## Review of medical records, images, specimens – Category 5

**For review of existing data:** provide a date range or an end date for when the data was generated. The end date can be the date this application was submitted to the IRB. Example: 01/01/1999 to 12/31/2015 or all records through mm/dd/yyyy.

**Date Range:** 12/29/2004 to 07/09/2013

Check all that apply (data includes medical records, images, specimens).

(5a) Only data that exists before the IRB submission date will be collected.

(5b) The study involves data that exist at the time of IRB submission **and** data that will be generated after IRB submission. Include this activity in the Methods section.

(5c) The study will use data that have been collected under another IRB protocol.

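### The baseline-to-3-month metabolite contrast groups participants by drinking that precedes the second sample, so it can flag alcohol's own effect as a marker of acamprosate response

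*Combined protocol and SAP*

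**What the plan says.** Analysis for Specific Aim 1b describes two metabolite analyses.

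- **Baseline levels.** The plan states that "associations between baseline metabolite concentrations and the time of abstinence since baseline will be evaluated by linear regression with age and gender as covariates". As a check on confounding, "regression models including baseline PHQ-9 scores and LFTs (AST, ALT, and GGT) will be compared with those without".
- **Change.** The first group is defined as follows: "Participants who provided paired blood samples will be classified as responders (maintenance of complete abstinence". The second group consists of "non-responders (any consumption of alcoholic beverages during the trial period), and their metabolite concentrations at baseline and at 3 months will be compared". The method and its purpose are then given: the comparison is made "by two-way ANOVA to detect any significant changes between the two time points and whether these changes differ significantly between groups".

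The genetic step that follows takes forward metabolites linked to length of sobriety or to secondary phenotypes. It does not say whether a metabolite found only by the change ANOVA qualifies.

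For the new trial, "Analysis for Aim 2b will use a similar strategy the analysis described above in aim 1b". That section adds an assessment of whether metabolites that predict outcome differ between acamprosate and placebo. It does not say whether this extends to change in metabolites.

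On sampling in the new trial: "Frequency of blood draw: three time points, Baseline, 1 and 3 month visits". The blood volumes described there include metabolomics, and Table 1 schedules TLFB at months 1, 2 and 3. Neither the Aim 1b nor the Aim 2b analysis section names a month-1 metabolite analysis.

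**The concern.** Non-responders are people who drank between the two samples, and responders are people who did not. The time-by-responder term therefore compares change with intervening alcohol against change without it. If alcohol raises or lowers a metabolite, that metabolite will tend to change differently in the two groups, whether or not it has anything to do with acamprosate. The PHQ-9 and liver-test adjustment uses baseline values and belongs to the regression models, so it does not address drinking during the trial.

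The Purpose/Background section treats change in plasma metabolites as a strong intermediate phenotype for finding genes. A metabolite that merely tracks recent drinking could be read as a response marker and, if the selection rule is read loosely, enter the metabolite GWAS. Aim 1b is the most exposed: all CITA participants took acamprosate (Table 2), and the background section acknowledges that, without a placebo arm, drug-specific associations could not be separated from other contributors to sobriety.

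**Working it through.** The plan gives no sample size, alpha or effect size for these tests, so there is no figure of its own to reproduce. The check asks how often the time-by-responder test is significant at two-sided 5% when the metabolite has no link to drug response but alcohol shifts it.

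**Inputs from the documents.** CITA has 445 participants in Aim 1b (443 in Table 2), with 132 abstinent at 3 months (ITT count, Table 2). About one third abstinent is the rate assumed for power under Aim 2a. The new trial enrols 800.

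**Assumptions.** There are 200 to 445 pairs (132 is not a count of paired samples). Within-person correlation is 0.5, so the SD of change is sqrt(2 × (1 − 0.5)) = 1. Alcohol shifts the level by d SD in a fraction f of non-responders who are drinking near the draw.

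**Formula.** z = f·d / sqrt([1 + f(1 − f)d²]/n_N + 1/n_R), where n_N and n_R are the numbers of non-responders and responders. The rejection rate is Φ(z − 1.96) + Φ(−z − 1.96).

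**Example** (n_R = 132, n_N = 445 − 132 = 313, d = 0.5):

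| f | z | False-positive rate |
|---|---|---|
| 0.3 | 0.15/0.1046 = 1.43 | 30% |
| 0.5 | 0.25/0.1047 = 2.39 | 67% |
| 0.8 | 0.40/0.1044 = 3.83 | 97% |

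**Simulation** (one third abstinent, constant lapse hazard, f = 0.6, 4,000 runs per setting), planned 3-month test:

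| d (SD) | 200 pairs | 300 pairs | 445 pairs |
|---|---|---|---|
| 0 | 6% | 5% | 6% |
| 0.25 | 18% | 23% | 32% |
| 0.5 | 52% | 67% | 84% |
| 0.8 | 87% | 97% | 100% |

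**Alternatives**, 300 pairs, d = 0.25 / 0.5 / 0.8:

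- Month-1 sample substituted with no restriction: 10% / 20% / 42%. Inflation remains, because under a constant hazard about 43% to 47% of non-responders have already lapsed by month 1 (for about 45% down to 30% abstinent at 3 months).
- Month-1 change only in those still abstinent at month 1 (landmark): 6% / 5% / 5%.
- Time × responder × arm interaction at 3 months, 2:1 allocation, same alcohol effect and drinking pattern in both arms: 5% / 5% / 5%.

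**Size of the landmark set.** With S(t) = exp(−ln 3 × (t/90)^k), S(30) = 0.693 for k = 1 and 0.530 for k = 0.5. Of 800, about 555 or 424 would be abstinent at month 1, before missed draws. The share lost is 31% or 47%. Of those retained, (1/3)/0.693 = 48% or (1/3)/0.530 = 63% stay abstinent to day 90, so both outcome groups are well filled.

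**The case against.** Several counter-arguments are sound and limit the point.

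**The placebo arm.** A reader might infer that placebo controls cannot help because relapsed placebo patients also drank. The reverse is true: an effect shared equally by both arms cancels in a responder-by-arm test of change. What remains open is whether the planned interaction covers change, and cancellation needs similar drinking among relapsers in the two arms. With 560 pairs, d = 0.5, and 50% against 80% drinking near the draw, the three-way test is falsely positive in about 13% of cases.

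**The size.** Any drinking counts as non-response, so one early lapse followed by sobriety is included. Calculations that shift every non-responder by the full amount give an upper bound. This stands, and is why f is varied above.

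**The route to the GWAS.** Length of sobriety is analysed with baseline samples, which precede drinking in the trial. The plan does not say that metabolites found only by the ANOVA go forward, nor that they do not.

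**The month-1 sample.** A reader might infer that Aim 1b neglects one. No month-1 CITA sample is documented, so the gap concerns Aim 2b only. The month-1 draw also serves GGT and acamprosate levels, so the blood itself is not idle.

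**Aim 3.** The plan says "we will obtain transcriptomic profiling and proteomic profiling for AUD subjects before and after 3 months of acamprosate therapy", and a reader might infer that post-treatment profiles will feed the predictive algorithm. The analysis of Aim 3 is deferred, and nothing says that those profiles will be predictors.

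**The remedy.** Adjusting for days since last drink would not work. Responders have roughly 90 days plus their abstinence before baseline, and lapsers have fewer, so the covariate nearly reproduces the grouping. The landmark conditions on early abstinence and answers a somewhat different question, so making it the sole main analysis would be a trade-off.

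**Conclusion.** The point holds for the baseline-to-3-month responder contrast. As written, that contrast cannot separate a marker of acamprosate response from a direct effect of alcohol, and the plan contains no control for this. It is most serious in Aim 1b, where no placebo comparison is possible. In Aim 2b the remedy may already be intended, but the text does not say so.

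Under the assumptions shown, a 0.5 SD alcohol shift with 60% of lapsers drinking near the draw gives about 52% to 84% false positives for 200 to 445 pairs. With 30% drinking, the analytic figure for 445 pairs falls to 30%. Neither the shift nor the proportion drinking is in the documents. The supported conclusion is that alcohol's effect can pass as a response marker, not that it will. The baseline-metabolite regression is unaffected by drinking during the trial.

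**What to change.** 1. **Aims 1b and 2b.** Label the baseline-to-3-month responder contrast descriptive, and state that metabolites found only by it are not sent to the metabolite GWAS.
2. **Sensitivity analysis, both aims.** Repeat the contrast in participants alcohol-free by TLFB for a fixed window (for example 30 days) before the 3-month draw, in place of any adjustment for days since last drink. This keeps earlier lapsers who were sober when sampled. It will be smaller, and does not remove alcohol effects that outlast the window.
3. **Aim 2b.** State that the treatment interaction covers metabolite change. Add a month-1 landmark analysis: among participants alcohol-free by TLFB up to the month-1 draw, relate baseline-to-month-1 change, and its interaction with arm, to abstinence from month 1 to month 3.

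**Cost.** Items 1 and 2 are analysis wording and use data already collected or scheduled. Item 3 adds no visits or blood draws, but the month-1 samples must be assayed, and the documents do not confirm that this is resourced. About 31% to 47% of participants would leave the landmark analysis under the assumed lapse curves, and its results apply to people who were abstinent through month 1. Early lapsers remain in the baseline-metabolite analysis.

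### The paired baseline and 3-month metabolite comparison names a two-way ANOVA with no within-person term; run as named, its tests of change and of difference in change are conservative and lose power

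*Combined protocol and SAP*

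**What the plan says.** Under Data Analysis, the section for Specific Aim 1b puts concentrations on a log scale ("Metabolite concentrations will be log-2 transformed") and describes two analyses. The first is a linear regression of time abstinent on the baseline concentration, with age and gender as covariates. The second uses two samples per person: "Participants who provided paired blood samples will be classified as responders" or non-responders, and "their metabolite concentrations at baseline and at 3 months will be compared by two-way ANOVA". The stated purpose of the second is "to detect any significant changes between the two time points and whether these changes differ significantly between groups".

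No participant effect, repeated-measures structure, within-subject error term or change score is named. The plan also does not say that the two samples will be treated as independent. For the new trial, "Analysis for Aim 2b will use a similar strategy the analysis described above in aim 1b", with an assessment of whether metabolomic predictors differ between acamprosate and placebo. Neither section gives a significance level, power, standard deviation, within-person correlation or number of pairs for this comparison.

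**The concern.** A two-way ANOVA on time and response group, without a participant term, takes its error from the full between-person spread. The questions asked are about change within a person, and stable differences between people cancel out of that. If a person's two values are positively correlated, the error term is too large for the time test and the time-by-response test.

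These are the two questions this analysis is meant to answer. The Purpose/Background section reports a preliminary pattern of the same kind: responders had higher serum glutamate at baseline, and it fell during treatment. A test with the wrong error term could miss such a pattern in data that are able to show it.

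**Working it through.** The plan gives no figure to reproduce, so the check is a derivation confirmed by simulation.

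**Inputs from the documents**
- Two values per participant, on the log2 scale (Analysis for Specific Aim 1b).
- The tests of interest are time and time by response (same section).
- Upper bound on the number of pairs: a "previously recruited CITA cohort of 445 acamprosate-treated alcoholic patients"; Table 2 lists 443 for CITA. The number with paired samples is not stated.
- Responder share: 29.7% abstinent at 3 months in CITA (Table 2, counting dropouts as relapsed). The share among those with pairs is not stated.

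**Assumptions**
- Two-sided 5% level, equal variance σ² at both times, and r from 0.1 to 0.7.

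**Derivation**
1. The variance of one person's change is 2σ²(1 − r). The ANOVA without a participant term uses 2σ².
2. Its test statistic for time or interaction is therefore the correct one multiplied by √(1 − r). It rejects only when the correct statistic exceeds 1.96/√(1 − r).
3. True level = 2 × [1 − Φ(1.96/√(1 − r))].
4. For an effect that the paired analysis detects with 80% power, the correct statistic has mean 1.96 + 0.84 = 2.80. Power = Φ(2.80 − 1.96/√(1 − r)).
5. The sample size needed for the same standard error, relative to the paired analysis, is 1/(1 − r).

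| r (assumed) | Effective cut-off | True level, time and interaction | Power (paired = 80%) | Sample-size multiple |
|---|---|---|---|---|
| 0.1 | 2.07 | 3.9% | 77% | 1.1 |
| 0.3 | 2.34 | 1.9% | 68% | 1.4 |
| 0.5 | 2.77 | 0.6% | 51% | 2.0 |
| 0.7 | 3.58 | 0.03% | 22% | 3.3 |

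Worked line for r = 0.5: 1.96/√0.5 = 2.77; level 2 × [1 − Φ(2.77)] = 0.6%; power Φ(2.80 − 2.77) = Φ(0.03) = 51%.

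**Responder main effect.** The same ANOVA understates this variance by the factor 1 + r. The true level is 2 × [1 − Φ(1.96/√(1 + r))], which is 6.2% / 8.6% / 11.0% / 13.3% at the four values of r.

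**Simulation** (6,000 replicates per setting; 120, 200 and 443 pairs; 30% responders)
- At r = 0.5 the ordinary two-way ANOVA had interaction power of 50% to 52% where the within-person analysis had 80%. Its level was 0.4% to 0.8% for time and interaction, and 10.8% to 11.2% for the responder main effect.
- The within-person analysis held 4.6% to 5.6% for all three tests across all settings.
- The results hardly changed with the number of pairs, so the missing count does not affect the conclusion.

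**The case against.** The strongest reply is that the authors mean a repeated-measures ANOVA. A time-by-group design with repeated measures is also a two-way ANOVA and is often called that. The text describes the samples as paired, keeps only people with both, and asks about change. A reader might infer that the plan certainly discards the pairing; the documents do not support that, since they never say the samples are treated as independent.

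The reply does not settle the matter. The wording allows two models that give different p-values on the same data. Where the authors want a linear mixed model, in the heritability analysis for Aim 1a, they name it.

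Three other readings are tempting and go too far:
- *The power loss is certainly large.* It depends on r. From 80%, the loss is about 3 points at r = 0.1, 12 at 0.3, 29 at 0.5 and 58 at 0.7.
- *The plan will produce excess false positives between responders and non-responders.* That would be true of a responder main-effect test from this ANOVA, but the plan does not list one. The regression on baseline concentration has one value per person and is unaffected.
- *False signals will pass into the genome-wide step.* That step starts from metabolites linked to length of sobriety or to secondary phenotypes. Length of sobriety is the outcome of the regression, and the text does not say that the ANOVA selects metabolites. For the two tests planned here, the error lies towards missed signals.

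**Conclusion.** The point holds in conditional form. The named method has no within-person term, and followed literally it gives wrong p-values for both questions the plan asks of it. For any positive r, with equal variances at the two times, the time and time-by-response tests are conservative. The loss is small at r = 0.1 (77% against 80%) and serious from about r = 0.5 (51%, equivalent to needing twice the sample). The documents do not show where in this range the metabolites lie. If the authors already intend a repeated-measures analysis, the defect is one of specification and the same correction removes it. The inflated level of the responder main effect is secondary, because that test is not planned.

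**What to change.** In the analysis for Aim 1b, replace the two-way ANOVA with a linear mixed model for log2 concentration, with a participant random intercept and terms for time, response and time by response. A repeated-measures ANOVA, or an analysis of each person's change, would also serve with two time points.

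In the analysis for Aim 2b, state the same model with treatment and its interactions added, since the model without treatment cannot show whether the patterns differ between acamprosate and placebo. Table 1 also schedules a blood draw at 1 month, so that section should say whether the 1-month sample enters the model.

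An ANCOVA of the 3-month level on response, adjusted for the baseline level, is not a suitable replacement. It does not test overall change. It also estimates a different quantity when responder groups, which are not randomised, differ at baseline, as the preliminary glutamate finding suggests they may.

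The cost is about one sentence in each section, with no new data.
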